#### **Product constituent testing:**

Pouches of used smokeless tobacco product will be obtained for chemical constituent analysis. Prior to the clinic visit at week 4 subjects will be asked to collect all used samples during the 24 hours before the visit. These samples will be placed in a small cooler and brought to the clinic visit. In addition, five unused oral tobacco pouches from their tin will be collected. Both these samples will be frozen. These samples will be shipped on dry ice to the CDC when samples from all the visits have been collected. At the CDC, the levels of selected chemical constituents in the unused and used pouch will be analyzed. These chemical constituents include nicotine, tobacco specific nitrosamine (NNK, NNN), BaP and catechols. Solanesol in cigarette filters will also be tested by CDC, which is a measure of tobacco smoke exposure (see 30, 31 for description of analysis conducted at CDC).

#### **Product intervention dose:**

The dose of unprotonated nicotine for Camel Snus Frost is 3.58, Camel Snus Mellow is 3.36, Camel snus Robust is 5.09 and Camel Snus Winterchill is 4.59 and our prior PK study (unpublished) showed that these doses led to levels that were about equivalent to or slightly higher than 4 mg medicinal nicotine lozenge. We will initiate use with the highest dose and if side effects are experienced, then we will assign the product with the lower dose. In our current study, the majority of smokers are able to tolerate the higher doses (95%; 21 out of 22 smokers)

and choose Winterchill (82%, 18 out of 22 smokers). The levels of exposure to toxicants (e.g., carcinogens) are lower than observed from cigarettes (2).

## **6.5 Potential Risks of Study Participation:**

The potential risks for subjects are minimal. Subjects' medical history will be reviewed at orientation prior to entry into the study. Subjects will be under medical supervision throughout their participation in the study and adverse symptoms will be recorded at each clinic visit and monitored by the PIs and study medical personnel. We will also be available 24 hours a day for emergency calls.

The major side effects associated with Camel Snus are nausea, dizziness and lightheadedness, mouth sores, gastrointestinal distress, headache, hiccups, dry mouth and sore throat. Nicotine is toxic to the fetus and pregnant women are excluded from participation.

The oral tobacco product administered to subjects is currently marketed and sold over-the-counter. All subjects are current regular smokers and thereby exposed to nicotine and tobacco toxicants. Oral tobacco products may be linked with an increased risk for oral and pancreatic cancer, although compared to cigarettes, the risk is dramatically less. The reduction in risk is largely due to delivery of lower number and sometimes levels of tobacco toxicants from smokeless tobacco to the user simply because the tobacco is not burned, which yields thousands of combustion products. However, as this study will examine, some users may maintain their baseline smoking rate while using oral tobacco thereby may increase their exposure to nicotine and perhaps some tobacco related toxicants. We will minimize this risk by seeing the subjects on a weekly and then bi-weekly basis to assess increased tobacco use. In addition, all subjects will be strongly advised to quit all tobacco use at the end of the study and will be provided cessation materials.

There is also the chance of continued use of the products after the study has ended; however, cessation of all tobacco products will be recommended to the subjects. If at any time the subject wants to quit smoking or use of all tobacco products, this decision will be encouraged and supported. Subjects will be provided with a treatment manual and referral to different treatments.

Other risks include blood draws and a trained laboratory technician or a registered nurse will obtain blood samples. Otherwise, the physiological and subjective measures will be noninvasive and should present no psychological or medical risk to the subject.

Some questionnaires may be of a sensitive nature assessing subjects' drug and alcohol use or psychiatric symptoms. Subjects will be told that they may refuse to answer, however, refusal may effect continued participation in the study.

## **7.0 Statistical Analysis**

This study has three primary aims: to determine the effect of instructions for use and the amount of substitution on biomarkers of exposure and patterns of oral tobacco use (primary endpoint at 4 weeks, but also assessed at 8 weeks), to determine when stabilization of product use occurs by examining the time effects for subjective, biological, topographic and behavioral responses (analysis for 2, 4, 6 and 8 weeks) and to determine important moderators for product use and exposure. Secondary aims include developing innovative measures to assess levels of exposure from smokeless tobacco and cigarettes.

Demographic and smoking history variables of those who entered the sampling phase and the trial phase will be summarized and compared to national survey data for the general population of smokers and smokers most interested in using oral tobacco products (e.g., 1). Baseline covariates will be summarized by treatment group to check that groups are balanced after randomization. Continuous measures will be summarized by mean (SD), median (range)

or other summary measures. Categorical covariates will be summarized by contingency tables. Numerical variables measured more than once at the baseline assessments will be assessed for reproducibility using the intra-class correlation coefficient and the average will be used for the baseline variable if adequate reproducibility is observed.

The primary outcome measures (tobacco use, biomarkers, subjective measures) will be assessed up to five times for each individual. The analysis of our primary aims will use linear mixed models to account for potential intra-subject correlation due to repeated measurements from a single individual. Linear mixed models are sensitive to miss-specification of the within-subject correlation structure. We will use exploratory graphical methods to identify the appropriate within-subject correlation structure. Residual plots and other diagnostic methods will be used to check other model assumptions.

**Hypothesis 1** will be analyzed by fitting a linear mixed model for each of the outcome measures (using week 6 as the primary endpoint): total NNAL, NNN, phenanthrene tetarol, mercapturic acids, PGEM, 8-epi-PGF2α, Total nicotine equivalents; and cardiovascular risk factors.. The mean model will include an effect for time, group and a time by group interaction. Specific hypotheses will be tested by testing the significance of the appropriate contrast. A secondary analysis will be completed adjusting for important factors such as environmental toxicant exposures, nutrition, stress and health to determine the effect their inclusion has on the association between group and the outcomes. Finally, we will complete an exploratory analysis that includes a site by group interaction to determine if the group effect changes by location.

**Hypothesis 2** will be analyzed by fitting separate linear mixed models for each group using biomarkers, snus topography, cigarettes and other subjective responses as the outcome. We will test for significant time effects and present plots of the outcomes to visually represent the time effects. Stabilization will be considered to have occurred when the variance between time-points does not exceed the coefficient of variation of the measures as assessed in the usual brand smoking group.

**Hypothesis 3** will be analyzed using a linear mixed effects models with a mean model that includes time, group and potential moderators (e.g., use patterns, age, sex, dependence, subjective responses, etc.). Interactions between group and the potential moderators will be included in the model and tested to determine if the potential moderator modifies the effect of group on the outcome (total nicotine equivalents, total NNAL).

**Hypothesis 4** will be evaluated using scatter plots and other visual methods. Associations will be summarized by Pearson's or Spearman's correlation coefficient, as appropriate, and formal inference will be completed using linear regression.

Compliance to the assigned treatment is a concern in this study. Our primary analysis will follow the intent-to-treat principle, where subjects are analyzed in the group they were randomized to regardless of compliance, to preserve the integrity of a randomized study. In addition, we will summarize compliance by treatment group and evaluate the correlation between compliance and baseline covariates to identify potential predictors of treatment compliance. Finally, we will complete a secondary analysis that accounts for non-compliance. A standard analysis adjusting for compliance in a regression setting is known to be susceptible to selection bias and, therefore, our secondary analysis will be completed using a principle stratification framework (56).

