## 2.0 SPECIFIC AIMS

### *Primary Aims:*

1. To compare product use patterns and biomarkers of exposure and effect based on differing instructions for oral tobacco use: a) complete substitution vs. partial substitution for cigarettes; and b) specific instructions for use vs. no instructions (*ad libitum* use).
2. To determine stabilization of product use by examining time effects for subjective (e.g., dependence), biological (e.g., biomarkers of exposure) and behavioral responses (e.g., smoking exposure and oral tobacco topography).
3. To determine important moderators of use of a product and exposure (i.e., consumer perception of the product and consumer response to the product after sampling [Project 3], nicotine metabolite ratio, nicotine dependence, gender, race and age).

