### **Hypotheses**

#### *Primary Aims:*

1. Instructions for use will lead to significant differences in patterns of use, which will be related to biomarkers of exposure.
2. Time in study will have an effect on outcome measures and will reach a plateau by at least 6 weeks.
3. Moderators for exposure will include pattern and intensity of tobacco product use. Pattern and intensity of product use will be affected by subjective responses to products,

perception of safety of the product, gender, race, age, degree of dependence and nicotine metabolism phenotype.

*Secondary Aim:*

4. Biomarkers of exposure will be related to levels of chemical constituents extracted from used oral tobacco pouch products in the complete substitution condition, plus levels of solanesol in filters in the partial substitution condition.

The outcome of this study will provide guidance on methods and measures that should be used in clinical trial assessments of tobacco products (e.g, MRTPs or new tobacco products). Furthermore, this study will novelly consider the interactions and effects of instructions of product use, perception and response to the product, and individual differences on product uptake and use and toxicant exposure.

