Another critical methodological issue that has not been addressed is the time to stabilization of product use and whether assessment of a product during the initial phase of use differs from assessments made after several weeks of use. Examining the effects of duration of use on biological, behavioral and subjective outcome measures is important because MRTP study lengths have ranged from one day to one year (4), and if stabilization of use patterns have not occurred, then only incomplete information is being learned. Recent studies conducted by tobacco industry scientists Roethig et al. (20) and Mendes et al. (21) suggest that stabilization may occur in the first few weeks of product switching, although no systematic study across different measures has been conducted. If stabilization occurs within a few weeks, then clinical trials assessing product use and exposure only need to be this short duration, reducing cost and subject burden, and enhancing compliance.

A third critical methodological question that has been inadequately addressed is the identification of individual factors that may moderate exposure. Examining these factors is important in order to identify variables that significantly influence the uptake of a product, how the product is used and extent of toxicant exposure. These data will help us to understand how a tobacco product might differentially affect subpopulations of smokers. It will also help determine the essential recruitment criteria for subjects in future studies that are examining these outcome variables (4). For example, if age is an important moderator variable, then future studies should have sampling strategies that account for age.

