### *Subjective outcome measures:*

- 1) Interactive Voice Response system will be used on a daily basis to record amount of product use, cigarette and other nicotine containing products and tobacco use status will be reviewed and recorded at each clinic visit;
- 2) Fagerstrom Test for Nicotine Dependence (FTND) (44);
- 3) Wisconsin Index of Smoking Dependence Motives is a multidimensional measure of dependence based on theoretically grounded motives for drug use and intended to reflect mechanisms underlying dependence and has been found to be related to smoking heaviness, DSM-IV symptoms of depression and relapse (45);
- 4) Minnesota Nicotine Withdrawal Scale (46);
- 5) Questionnaire of Smoking Urges, a 32-item questionnaire on smoking urges, assesses a multidimensional conceptualization of craving to smoke (47);
- 6) Adverse Events Scale assesses the nature, severity, duration, action taken, and outcome of adverse events related to tobacco product use;
- 7) Perceived Health Risks Assessment asks subjects to rate their perception of their usual tobacco product against the study product to which they were randomly assigned;
- 8) Product Evaluation Scale is a 7-point Likert-type scale that is modified from the Cigarette Evaluation Scale (48). In addition, items from a scale that was used to evaluate various medicinal nicotine products is incorporated in the Product Evaluation Scale (49). This scale has been used in a number of our studies. Cigarette Evaluation Scale will be used at baseline;
- 9) Drug Effects/Liking Questionnaire (50);
- 10) Stages of Change (51);
- 11) Consumer Product Perception. This measure will be developed by Project 3 of this U19 and include cognitive and affective measures and Odor/Haptics; and
- 12) Tobacco Purchase Task. Participants will be asked "How much would you be willing to pay for one tin of Camel Snus?" As a reference point, participants are also asked to report how

much they usually pay for one pack of cigarettes. The ratio of these prices can give an indication of the relative value of Camel Snus, and would allow comparison across the study sites, where cigarette prices vary. Subjects will also be provided the Tobacco Purchase Task developed, which will be used to generate demand curves by asking participants to report the number of units of a tobacco product that they would consume in a day if the units cost various amounts of money. This procedure has been used to study demand for cigarettes (52-53).

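### The stated stabilization analysis uses weeks 2, 4, 6 and 8 only, so settling of product use, CO and some scales before week 2 cannot be dated, although the data are collected

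*Combined protocol and SAP*

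**What the plan says.** Primary aim 2 in section 2.0 is "To determine stabilization of product use by examining time effects for subjective (e.g., dependence), biological (e.g., biomarkers of exposure) and behavioral responses". The matching hypothesis is "Time in study will have an effect on outcome measures and will reach a plateau by at least 6 weeks". Section 7.0 restates the aim as finding the point at which use settles and names "subjective, biological, topographic and behavioral responses (analysis for 2, 4, 6 and 8 weeks". It adds that the primary outcomes, tobacco use among them, "will be assessed up to five times for each individual". Baseline plus those four weeks would make five, though that reading is an inference.

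The later Hypothesis 2 paragraph of section 7.0 describes a mixed model for each group, a test of time, plots and a stabilization rule. It names no weeks.

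Collection is denser than the stated grid:
- **Use:** "Interactive Voice Response system will be used on a daily basis to record amount of product use, cigarette and other nicotine containing products". The clinic-visit procedures in section 6.4 continue the diaries through the experimental period.
- **CO:** section 6.4 and Table 2 place it at every visit. The intervention visits are at weeks 1, 2, 3, 4, 6 and 8.
- **Scales:** Table 1, as far as its layout can be read, has several scales at week 1, including dependence, withdrawal, urges and product evaluation. At week 3 it shows only adverse events, the diary and the use summary.
- **Biomarkers:** blood and urine are collected at weeks 2, 4 and 8, with urine alone at week 6. Section 6.4 sends the week 4 and 8 samples for assay and stores those from week 2.
- **Topography:** week 4 only.

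**The concern.** Section 3.0 gives the reason for studying stabilization. It asks "whether assessment of a product during the initial phase of use differs from assessments made after several weeks of use", reports that "stabilization may occur in the first few weeks of product switching", and argues that early stabilization would let later trials be shorter and cheaper. The first two weeks are therefore a period of practical interest. In this trial, evidence on that period can come only from the diaries, CO and the week-1 scales, because assayed biomarkers and topography start at week 4. The stated grid leaves out the week 1 values of those measures, and the week 3 values of use and CO. A future designer could then learn that two weeks is long enough but not whether one week would have been.

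**Working it through.** The plan gives no figure for this point, so there is none to reproduce. The check compares time grids and then adds two illustrations.

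**1. Grids.** The stated analysis has weeks 2, 4, 6 and 8. The visits are at weeks 1, 2, 3, 4, 6 and 8, so the stated grid uses 4 of 6 CO visits. If each diary value is the mean of the preceding seven days, it also uses 4 of 8 weekly values for use.

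**2. Dating interval.** If a measure settles at time s, the grid can only place s between two adjacent points.

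| True s (weeks) | Stated grid | Visit grid (CO) | Weekly diary means (use) |
|---|---|---|---|
| 0.5 or 1 | 0–2 | 0–1 | 0–1 |
| 1.5 or 2 | 0–2 | 1–2 | 1–2 |
| 2.5 or 3 | 2–4 | 2–3 | 2–3 |
| 3.5 or 4 | 2–4 | 3–4 | 3–4 |
| 5 | 4–6 | 4–6 | 4–5 |
| 6 | 4–6 | 4–6 | 5–6 |

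This step needs no assumption about the shape of the curve.

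**3. Illustration with adjacent changes.** Assume f(t) = 1 − exp(−3t/T), where T is the week at which 95% of the change is complete. Call a measure stable at the first adjacent pair whose change is at most 0.10 of the total. Both choices are assumptions. The plan's own rule refers to variability in the usual-brand group, and the documents give no value for it.

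- **Stated grid, weeks 2 to 4:** the change is 0.000 for T = 0.5, 1.000 − 0.998 = 0.002 for T = 1, 1.000 − 0.982 = 0.018 for T = 1.5, and 0.998 − 0.950 = 0.048 for T = 2. All four give the same answer: stable from the first pair.
- **Visit grid, weeks 1 to 2:** the change is 1.000 − 0.998 = 0.002 for T = 0.5 and 0.998 − 0.950 = 0.048 for T = 1, so both are stable at weeks 1–2. It is 0.982 − 0.865 = 0.117 for T = 1.5 and 0.950 − 0.777 = 0.173 for T = 2, so both are first stable at weeks 2–3.
- **Slow settling, T = 6:** the stated grid gives weeks 4–6 (0.950 − 0.865 = 0.085). The visit grid gives weeks 3–4 (0.865 − 0.777 = 0.088), when 1 − 0.777 = 0.223 of the change was still outstanding at week 3. A fixed tolerance is easier to meet over a shorter interval, which matters for the fix.

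**4. Illustration with half-times.** Let h be an assumed half-time in days. The mean of 2^(−t/h) over each seven-day block is the share of the change still outstanding.

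| h (days) | Week 1 | Week 2 | Week 3 | Week 4 |
|---|---|---|---|---|
| 2 | 0.314 | 0.028 | 0.002 | 0.000 |
| 3 | 0.441 | 0.087 | 0.017 | 0.003 |
| 5 | 0.597 | 0.226 | 0.086 | 0.032 |
| 7 | 0.686 | 0.343 | 0.172 | 0.086 |

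With h of 2 to 3 days, nearly all the movement is over before the week 2 value. With h of 5 to 7 days, the stated grid still sees a clear fall from week 2 to week 4: 0.226 to 0.032, and 0.343 to 0.086.

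**The case against.** The strongest reply is that the plan never bars the early data. The weeks stand in a parenthesis within a summary of aims, the operative Hypothesis 2 paragraph names none, and collecting more often than one analyses is not a contradiction. Diaries also serve compliance and payment, early visits also serve safety, and weeks 2, 4, 6 and 8 are the scheduled urine collections, so a common grid is defensible. This stands in part: the limit is in the stated analysis and not in the data. But a paragraph that is silent on weeks does not lift a limit set earlier in the same section.

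A second reply is that baseline against week 2 already covers the early period. That contrast mixes the switch of product with settling afterwards. The first comparison that lies wholly after the switch is week 2 to week 4.

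A third reply is that the half-time figures are assumed, and this is correct. No section supports an exponential curve or half-times of a few days, and the mapping from diary days to analysis weeks is undefined. If the week 2 value averaged days 1 to 14, the shares outstanding would be (0.314 + 0.028)/2 = 0.171 for h = 2 and (0.441 + 0.087)/2 = 0.264 for h = 3, so week 1 would enter after all.

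A reader might infer that stabilization cannot be dated at all, or that the stabilization aim fails. The documents do not support this: stability by week 2, later settling to within two weeks and a plateau by week 6 can all be examined. A reader might also take the contrast of early with later use to be the wording of aim 2. It is in the background; the aim speaks of time effects.

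**Conclusion.** The point holds for cigarette and snus use, CO and the scales collected at week 1. Under the analysis as stated, stabilization before week 2 cannot be dated, and later stabilization is dated to within about two weeks. For use and CO, data already scheduled would halve that interval to one week over the first four weeks. For the scales the gain is at week 1 only.

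It would be wrong to extend this to biomarkers or topography. Their time points are set by sampling and assay, so a change of analysis weeks gains nothing. The topography data come from week 4 alone, although section 7.0 lists topographic responses for four weeks; that is a separate gap.

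The dating intervals follow from the schedule alone, apart from the reading of a weekly diary value as the preceding seven days. The 10% tolerance, the exponential curve and the half-times are illustrations under assumption, not estimates. The change is worth making before analysis because it also removes a later choice of time points.

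**What to change.** In section 7.0, in both the summary of aims and the Hypothesis 2 paragraph, state the time points by measure:
- **Cigarettes and pouches:** weekly means of the daily diary for weeks 1 to 8, with the days that make up each week defined.
- **CO:** all visits, at weeks 1, 2, 3, 4, 6 and 8.
- **Subjective scales:** every visit at which each scale is actually collected, including week 1 where scheduled.
- **Biomarkers and topography:** unchanged.

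Apply the stabilization assessment from week 1 for the first three groups, and limit the statement about five assessments to the measures it fits. Because visits are unequally spaced, express the allowed change over a common interval, so that a one-week gap is not easier to pass than a two-week gap.

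The cost is a wording change and a few more repeated measures per subject in the same models, with a correlation structure that suits unequal spacing. No new data collection is needed.

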#### **Sample-size determination.**

A sample of size 138 per group (690 in the five groups) would be required to assure an 80% chance of demonstrating that complete substitution leads to higher reduction in NNAL levels compared to the partial substitution after controlling for baseline NNAL levels (assuming a correlation of 0.6 between baseline and follow-up NNAL scores, and an effect size of low to medium) and accounting for drop-out rates and an abstinence rate of 40 to 50%. See Human Subjects section for details.

**Randomization:** Stratified randomization will be generated by the Biostatistics and Informatics Core of this grant.

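### The trial is sized on a baseline-adjusted NNAL comparison, but the Hypothesis 1 model lists no baseline term and neither randomisation factor

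*Combined protocol and SAP*

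**What the plan says.** All the analysis text is in section 7.0 of the combined protocol and SAP.

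- **Model.** Under Hypothesis 1: "The mean model will include an effect for time, group and a time by group interaction". A secondary analysis adjusts for an open-ended list of influences (environmental exposure, diet, stress, health). Site appears only in an exploratory interaction with group.
- **Sizing.** The sample-size paragraph gives 138 per group (690 in five groups) for 80% power to show a greater NNAL reduction with complete than with partial substitution, "after controlling for baseline NNAL levels (assuming a correlation of 0.6 between baseline and follow-up NNAL scores"), and "accounting for drop-out rates and an abstinence rate of 40 to 50" per cent. For the rest it says "See Human Subjects section for details"; that section is not in the supplied text.
- **Baseline variable.** For measures taken more than once at baseline, "the average will be used for the baseline variable if adequate reproducibility is observed". Table 2 marks total NNAL at both baseline visits.
- **Outcome vector.** The primary outcomes "will be assessed up to five times for each individual".
- **Visit.** The opening of section 7.0 has "primary endpoint at 4 weeks, but also assessed at 8 weeks"; Hypothesis 1 has "using week 6 as the primary endpoint".
- **Strata.** Section 6.3 and the randomisation text in section 8.2 stratify by site and by cigarettes per day, cut at 18.

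**The concern.** The sample-size paragraph describes one analysis and the Hypothesis 1 sentence lists the terms of another. A mean model with free time, group and time-by-group effects gives each arm its own mean at every visit. If only post-baseline visits are in the outcome vector, baseline is unused. If baseline visits are in it, a baseline-referenced contrast is change from baseline, not baseline adjustment. Only a baseline covariate or a baseline mean constrained to be equal across arms would deliver the comparison used for sizing, and neither is stated.

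Precision is at stake, along with a choice left open: level, change and adjusted analyses all fit some part of section 7.0, and the choice would arise for each of several biomarkers. The randomisation factors are also absent from the primary model. The cigarettes-per-day stratum appears nowhere in section 7.0.

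**Working it through.** **The plan's own figure.** 138 × 5 = 690 checks. The 138 cannot be reproduced uniquely, because alpha, a numerical effect size, dropout and the use of the abstinence rate are not given. It is not shown to be wrong. For example, a standardised effect of 0.30, two-sided 5% and adjustment give 2 × 0.64 × 2.802² / 0.30² ≈ 112, and 112 / 0.80 = 140 with an assumed 20% dropout. What follows takes 138 per group = 80% with adjustment as given.

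**Inputs.** Correlation 0.6 (sample-size paragraph). Assumed: two-sided 5%, equal variances, the same arms compared, and between-baseline correlation rb of 0.6, 0.7 or 0.8.

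**Anchor.** Non-centrality 1.960 + 0.842 = 2.802 at adjusted variance 1 − 0.6² = 0.64 (follow-up SD = 1). For a contrast with variance V, power = Φ(2.802 × √(0.64/V) − 1.960).

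**Level contrast and single baseline**

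- Level only: V = 1.00; Φ(2.242 − 1.960) = 61%.
- Change from one baseline: V = 2(1 − 0.6) = 0.80; Φ(2.506 − 1.960) = 71%. Variance ratio, adjusted to change: 0.64/0.80 = 0.80. So 138 with adjustment is worth 138/0.80 ≈ 172 with change.

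**Mean of two baselines.** Its variance is Vb = (1 + rb)/2 = 0.80, 0.85 or 0.90. The plan does not say whether 0.6 is a single-visit correlation or the correlation with the mean, so both are shown.

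| Reading of 0.6 | rb | Change variance | Power, change | Adjusted variance | Ratio | 138 adjusted is worth |
|---|---|---|---|---|---|---|
| Single visit | 0.6 | 0.600 | 82% | 0.550 | 0.917 | 151 |
| Single visit | 0.7 | 0.650 | 79% | 0.576 | 0.887 | 156 |
| Single visit | 0.8 | 0.700 | 76% | 0.600 | 0.857 | 161 |
| With the mean | 0.6 | 0.727 | 75% | 0.640 | 0.881 | 157 |
| With the mean | 0.7 | 0.744 | 74% | 0.640 | 0.861 | 160 |
| With the mean | 0.8 | 0.762 | 73% | 0.640 | 0.840 | 164 |

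Single-visit rows use 1 + Vb − 1.2 for change and 1 − 0.36/Vb for adjustment. The other rows use 1 + Vb − 1.2√Vb and 0.64. A generalised least squares calculation with two baselines and weeks 4 and 8 as outcomes gives the single-visit change variances when arm means are free, and the adjusted variances when the baseline mean is common to the arms.

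**Unequal variances.** If a share p = 0.4–0.5 of the complete-substitution arm is abstinent and its mean is lower by D = 1–2 SD (D assumed), that arm's variance rises by p(1 − p)D². The variance reductions from adjustment shrink to about 12–17% (single baseline) and 5–14% (two-visit mean). The order is unchanged.

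**Pooled arms.** If two arms are pooled per side and 138 was a one-arm figure, each non-centrality is multiplied by √2. Power is then 98–99% adjusted, 94% for single-baseline change and 95–98% for two-visit change. The level contrast gives Φ(2.242 × 1.414 − 1.960) ≈ 89%.

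**Strata.** The documents give no variance share for site or cigarettes per day, so no gain is claimed. Baseline NNAL may already carry part of it.

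**The case against.** The strongest reply is that section 7.0 should be read as a whole. The sample-size paragraph belongs to it and says baseline is controlled, and the same section defines a baseline variable. The list of terms under Hypothesis 1 is not called exhaustive. This stands in part: a reader might infer that the plan excludes baseline or never mentions it, and the documents do not support that. The section is incomplete and does not agree with itself. But the Hypothesis 1 sentence is the only specification of that mean model, and it does not place the baseline variable in it.

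Second, the outcome count does not prove that a change analysis is planned. Table 2 marks NNAL five times (two baseline visits and weeks 2, 4 and 8). However, section 6.4 stores the week 2 samples for possible later analysis, and the count of five covers tobacco use and subjective measures too. This stands, which is why the level and change readings are both shown.

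Third, the planned average of two baselines removes much of the loss, and pooled arms leave ample power. This also stands. It limits the shortfall against 80% but does not alter the advantage of adjusting for the same baseline.

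Fourth, a reader might infer from sections 6.3 and 8.2 that the plan promised to handle the strata and then dropped them. Those sentences concern imbalance on factors other than the strata, and Hypothesis 1 has an open-ended secondary adjustment. What remains is that the primary model does not list the factors used to randomise.

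**Conclusion.** The point holds as a gap between the analysis used for sizing and the model as listed, and it should be fixed. Adjusting for the same baseline is more precise than the level or change contrast in every scenario examined, by 20% of variance against single-baseline change and 8–16% against two-visit change under equal variances. The power figures (61%, 71%, 73–82%) are conditional on 138 giving 80% with adjustment, two-sided 5% testing and the assumed between-baseline correlations.

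Two stronger conclusions are not supported. The documents do not show that the trial is underpowered: the shortfall may be nil with the two-visit mean, every change or adjusted option is at least 94% under the pooled reading, and the inputs behind 138 are in a section not supplied. Nor is there a bias, because the randomised comparison stays valid without these terms.

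**What to change.** In the Hypothesis 1 model for each biomarker:

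1. State how baseline enters. Either include the baseline variable already defined in section 7.0 as a covariate (the mean of the two baseline visits where both are assayed and reproducible), or use a constrained longitudinal model with a common baseline mean across arms.
2. Add site and cigarettes-per-day stratum (≤18, >18) as fixed effects.
3. State whether the complete versus partial contrast pools the two arms on each side.
4. Reconcile the primary visit, week 4 in one place and week 6 in another. Table 2 marks no NNAL at week 6, and section 6.4 says that samples from weeks 4 and 8 are analysed.
5. If the model is left unadjusted, restate the power for that model, using the inputs in the Human Subjects section.

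The cost is a few sentences in section 7.0, with no added visits or participants. The two-visit mean needs NNAL assayed at both baseline visits. Table 2 marks both, but the Measures section allows for only some of the biomarkers to be analysed, so this should be confirmed.
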